4.2. Schedule of Events

Table 1:Schedule of Events

Assessment	Screening Visit ^a	Screening Period (2 Weeks +14 Days)	Randomization Visit ^a (Week -4)	DMF-GI Monitoring Period (up to 28 Days)	Wk 0 ^{a,b}	Wk 2 ^c	Wk 4 ^a	Wk 8 ^c	Wk 10 ^a /ET	Safety Follow- Up ^d (± 5 days)
Clinic Visit	Х		х		Х	х	х	Х	Х	
Informed Consent	Х									
Eligibility Criteria	Х		X ^e							
Demographics	Х									
Vital signs ^f	Х									
Medical History (incl. MS disease status) ^g	Х									
Alcohol Consumption	Х									
Tobacco Use	Х									
Pregnancy Testing ^h	Х		х							
Concomitant Medications/ Procedures	Х		х		х	х	х	х	х	Х
Blood Biomarkers (optional) ^j			х				Х		Х	
Dispense eDiary	Х									
eDiary Training	Х									
eDiary Entries (Daily) ^k										
Return eDiary to Clinical ^l			X ^m	X ^m					х	

Version 3

Protocol 109MS414 Phase 4 Study of GI Tolerability in DMF-Treated Subjects With Relapsing Forms of MS

Assessment	Screening Visit ^a	Screening Period (2 Weeks +14 Days)	Randomization Visit ^a (Week -4)	DMF-GI Monitoring Period (up to 28 Days)	Wk 0 ^{a,b}	Wk 2 ^c	Wk 4 ^a	Wk 8 ^c	Wk 10ª/ET	Safety Follow- Up ^d (± 5 days)
Dispense DMF With Dosing Instructions			Х							
DMF Administration (Daily)			DMF administration will occur every day as per the USPI							
Randomization			Х							
Dispense Randomized Study Treatments			X ⁿ							
Randomized Study Treatment Administration (Daily)					Randomized study treatment administration will occur every day as per the prescribing information.					
SAEs	SAE data will be collected from the signing of the informed consent up to the Safety Follow-Up Telephone Interview. MS relapses resulting in hospitalization are considered SAEs but will not be reported as SAEs in the study unless the relapse is complicated by other SAEs or is fatal.									
AEs				AE data will be collected from the first dose of DMF up to the Safety Follow-Up Telephone Interview.						

Note: Weeks 2, 4, and 8 will have a visit window of ± 2 days, and Week 10 will have a visit window of ± 3 days.

Abbreviations: AE = adverse event; DMF = dimethyl fumarate; DNA = deoxyribonucleic acid; eDiary = electronic diary; EDSS = Expanded Disability Status Scale; ET = early termination; GI = gastrointestinal; GSRS = Gastrointestinal Symptom Rating Scale; (Compared to the state of th

; MS = multiple sclerosis; ; RNA = ribonucleic acid; SAE = serious adverse event; USPI = United States Prescribing

Information;Wk = week.

^a This visit must be performed in clinic.

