5.1.2. Clinical Experience With Dimethyl Fumarate

Clinical Pharmacokinetic Studies

In single-dose and short-term multiple-dose studies in healthy volunteers and subjects with MS, DMF was rapidly converted to its major metabolite (MMF) upon oral administration. Exposure (maximum plasma concentration and area under the curve) was generally dose proportional across the dose range (120 to 360 mg) and dosing frequencies (twice daily and 3 times daily) studied. No accumulation of exposure was detected with repeated dosing due to rapid elimination of the drug. In these studies, DMF was most frequently associated with flushing; no serious adverse events (SAEs) or deaths in healthy volunteers who received DMF were reported.

Clinical Efficacy and Safety in Multiple Sclerosis

The DMF clinical development program at the time the DMF marketing authorization applications were filed included 6 clinical studies in subjects with MS. In 4 of the studies (Phase 2 and 3 placebo-controlled efficacy and safety studies and their uncontrolled extensions), 2513 subjects with relapsing-remitting multiple sclerosis (RRMS) received DMF and were followed for periods up to 6 years, with an overall exposure of 6133 patient-years. Approximately 1056 subjects received >2 years of treatment with DMF.

Study C-1900 was a Phase 2, randomized, multicenter, placebo-controlled, double-blind, parallel-group, dose-ranging study composed of 2 parts: a 24-week double-blind, placebo-controlled safety and efficacy phase (Part 1) followed by a 24-week dose-blinded, safety extension phase (Part 2). The primary efficacy endpoint was the total number of new gadolinium

CONFIDENTIAL

(Gd)-enhancing lesions at Weeks 12, 16, 20, and 24 (calculated as the sum of the 4 magnetic resonance imaging [MRI] scans). A total of 257 subjects were randomly assigned to receive 120 mg DMF once daily, 120 mg DMF 3 times daily, or 240 mg DMF 3 times daily. Subjects treated with 240 mg DMF 3 times daily had a 69% reduction in the mean number of new Gd-enhancing lesions versus placebo as measured on monthly MRI from Weeks 12 to 24 of the study, and a 48% and 53% reduction in new or enlarging T2 hyperintense lesions and new nonenhancing T1 hypointense lesions at Week 24 compared with placebo, respectively.

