7.2.4. DMF-GI Monitoring Period

The duration of the DMF-GI Monitoring Period will be up to 28 days. On the first full day after the Randomization Visit, subjects will start taking DMF per the prescribing instruction. Subjects

CONFIDENTIAL

will make daily entries in the eDiary, recording pertinent information regarding GI-related events to allow the characterization of events that occur while taking DMF. During this period, if a subject meets the threshold of a GSRS score of ≥ 3 in 1 question for 1 day or a GSRS score of ≥ 2 in 1 question for 2 consecutive days, the subject will receive an alert through his/her eDiary to begin taking the randomized study treatment the same day. Any subject who does not reach the GSRS threshold during the DMF-GI Monitoring Period will be discontinued.

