15.2. Monitoring and Recording Events

15.2.1. Adverse Events

Any non-SAE (including flushing) experienced by the subject between the time of first dose of study treatment and the Safety Follow-up Telephone Interview is to be recorded on the CRF, regardless of the severity of the event or its relationship to study treatment.

There are 2 exceptions to this:

CONFIDENTIAL

- Any GI-related AE experienced by the subject between the time of the first dose of DMF and study completion is to be recorded by the subject in his/her eDiary. Any GI AEs that lead to permanent study discontinuation or withdrawal or are serious must be recorded.
- Non-SAEs of MS relapse will not be collected unless leading to permanent treatment discontinuation or study withdrawal.

Nonserious GI AEs should be recorded in the eDiary and not in the eCRF.

For subjects who permanently discontinue DMF during the study, AEs should be recorded through the Safety Follow-Up Telephone Interview conducted 2 weeks (±5 days) after the subjects' Final Clinic Visit.

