2 STUDY OBJECTIVES AND ENDPOINTS

2.1 Primary Objective and Endpoint

The primary objective of this study is to evaluate whether Montelukast can reduce the severity of gastrointestinal (GI) events, measured by the Gastrointestinal Symptom Rating Scale (GSRS), after oral administration of Dimethyl Fumarate (DMF) in subjects with relapsing forms of multiple sclerosis (MS).

The primary endpoint of this study is the proportion of subjects with a worsening in the severity of GI adverse events (AEs), measured by the average change from Day 0 to Day 10 in GSRS score. If a patient takes the randomized study treatment one day after his or her GSRS score reaches the GI threshold, Day 0 is defined as the day prior to the first dose of randomized study treatment. If a patient takes the randomized study treatment on the same day when the GSRS score reaches the GI threshold, Day 0 is defined as the day with the first dose of randomized study treatment. If a patient missed the randomized study treatment for a few days after the GSRS score reached the GI threshold, Day 0 is the day immediately prior to the first dose when the GI threshold was reached. Day 10 is defined as 10 days after Day 0.

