Average change of GSRS score from baseline (Day 0) to Week 1, 2, 3, 4, 5, 6 and 8 will be summarized; a repeated measures model for the change of the GSRS score from baseline, adjusted for age, weight and baseline GSRS score, will be used to estimate effect at each time point. Sensitivity analyses using ANCOVA model for the average change may be performed.

Average change of GSRS score from Day 0 to 72 hours from the initiation of randomized study treatment

Average change of GSRS score from baseline (Day 0) to 72 hours (Day 3) from the initiation of randomized study treatment will be summarized and analyzed by the repeated measures method. No sensitivity analysis will be performed.

Proportion of subjects who take GI symptomatic therapy during the study

From Day 10 onward, subjects are allowed to use symptomatic therapy to treat DMFrelated GI events. The proportion of subjects who take GI symptomatic therapy from Day 10 to Week 10 will be summarized by treatment and analyzed using the Chi-squared test.

[figure not shown]
Percentage of subjects who discontinue DMF therapy due to the GI-related adverse events from Day 0 to Week 10

The proportion of subjects who discontinue DMF due to the GI-related adverse events from Day 0 to Week 10 will be summarized by treatment and analyzed using the Chi-squared test.

Proportion of subjects who experience flushing events

The proportion of subjects who experience flushing events from Day 0 to Week 10 will be summarized for the modified ITT population by treatment group and analyzed using the Chi-squared test. Flushing event as defined as an event coded to any of the following preferred terms: Flushing, Hot flush (under SOC of Vascular disorders), Erythema, Generalized erythema, Skin burning sensation (under SOC of Skin and subcutaneous tissue disorders), Burning sensation (under SOC of Nervous system disorders), Feeling hot (under SOC of General disorders and Administration site conditions), Hyperaemia (under SOC of Vascular disorders).

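### Flushing is compared by an unstratified chi-squared test although run-in flushing on DMF is already recorded; stratifying by it would gain precision at almost no cost

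*Combined protocol and SAP*

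**What the plan says.** - **Endpoint and test.** SAP 7.3.4 states: "The proportion of subjects who experience flushing events from Day 0 to Week 10 will be summarized for the modified ITT population by treatment group". The proportions are then "analyzed using the Chi-squared test. Flushing event as defined as an event coded to any of the following preferred terms", followed by a list of terms. The paragraph names no stratum, covariate or onset condition.
- **DMF comes first.** Protocol 7.2.4: "On the first full day after the Randomization Visit, subjects will start taking DMF per the prescribing instruction", and "The duration of the DMF-GI Monitoring Period will be up to 28 days". Montelukast or placebo starts only when the GI threshold is met within that period.
- **Flushing is expected on DMF.** Protocol 5.1.2, on the pharmacokinetic studies: "DMF was most frequently associated with flushing".
- **Run-in flushing is collected.** Protocol Table 1: "AE data will be collected from the first dose of DMF up to the Safety Follow-Up Telephone Interview". Protocol 15.2.1 puts on the CRF "Any non-SAE (including flushing) experienced by the subject between the time of first dose of study treatment and the Safety Follow-up Telephone Interview". The synopsis names DMF as the study treatment, so the two agree if the term is read that way.
- **Day 0.** For subjects who start the day after reaching the threshold, SAP 2.1 says "Day 0 is defined as the day prior to the first dose of randomized study treatment".
- **Treatment emergence.** SAP 7.4.2.1 counts an event already present before montelukast/placebo only if it later worsened. The rule is written for the safety populations. The flushing paragraph uses the modified ITT population and does not refer to it.

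**The concern.** The effect of montelukast on flushing is a stated secondary objective. At Day 0 the modified ITT population is a mixture of subjects who have already flushed on DMF and subjects who have not, and the two groups probably differ widely in their chance of flushing over the next ten weeks. The planned test leaves that difference in the error term.

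The SAP adjusts for the pre-treatment value elsewhere: the analyses of GSRS change and of time to first worsening include the Day 0 score. Flushing has an equivalent baseline value in the adverse event data, and it is not used. What is at stake is precision, the more so because SAP section 5 closes enrollment at about 60 dosed subjects, roughly 30 per arm instead of 59.

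**Working it through.** **The plan's own figure.** The only sample-size figure is for the primary endpoint: 59 per arm, about 80% power, 40% against 70% improving, 15% early discontinuation. Counting those who discontinue as non-improvers gives 0.85 × 40% = 34% and 0.85 × 70% = 59.5%. With mean 0.4675 and difference 0.255:

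n = [1.96·√(2·0.4675·0.5325) + 0.8416·√(0.34·0.66 + 0.595·0.405)]² / 0.255² = 58.9, so 59 per arm.

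The stated figure reproduces on this reading. No power is stated for flushing.

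**Assumptions for flushing (none is in the documents).** q = share who flush in the run-in; h = probability of flushing after Day 0 in those subjects; l = the same in the others.

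**Step 1, variance.** The unstratified variance per subject is p(1−p), with p = q·h + (1−q)·l. The within-stratum variance is q·h(1−h) + (1−q)·l(1−l).

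| Scenario | q | h | l | p | p(1−p) | Within strata | Reduction |
|---|---|---|---|---|---|---|---|
| A | 30% | 50% | 20% | 0.290 | 0.2059 | 0.1870 | 9% |
| B | 30% | 60% | 15% | 0.285 | 0.2038 | 0.1613 | 21% |
| C | 30% | 70% | 10% | 0.280 | 0.2016 | 0.1260 | 38% |
| D | 40% | 80% | 10% | 0.380 | 0.2356 | 0.1180 | 50% |

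**Step 2, power if montelukast halves flushing in both strata.** Simulation, 200,000 runs per cell, 2-sided 5%. CMH sums, over the two strata, the observed minus expected events in one arm (expected = n₁T/N), and divides by the square root of the summed n₁n₂T(N−T)/[N²(N−1)].

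| Scenario | Chi-squared, 59/arm | CMH, 59/arm | Chi-squared, 30/arm | CMH, 30/arm |
|---|---|---|---|---|
| A | 50% | 51% | 27% | 28% |
| B | 49% | 53% | 27% | 30% |
| C | 48% | 58% | 26% | 33% |
| D | 64% | 81% | 37% | 51% |

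**Step 3, if montelukast has no effect in run-in flushers** and halves flushing in the others (59/arm): chi-squared 14, 10, 8 and 6%; CMH 15, 11, 8 and 8%. The gain is under 2 points because little difference is left to find: in D it is 0.6 × 5 points = 3 points.

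This depends on the assumed rates. Take 30% against 15% in subjects without run-in flushing, q = 30%, and every run-in flusher flushing again. The contrast is then 51% against 40.5%, and power goes from 21% to 37% at 59 per arm and from 13% to 21% at 30. If montelukast instead lowers flushing by the same 15 points in run-in flushers (60% to 45%), the gain at 59 per arm is small, 43% to 45%.

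**Step 4, type I error.** With no effect in either stratum (A to D, both sizes): chi-squared 4.8–5.2%, CMH 4.8–5.1%.

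**Step 5, counting only new-onset or worsened flushing.** Limiting case: all later flushing in run-in flushers is recorded as ongoing and not worsened, so none of it counts. Power of the stratified test at 59 per arm is 24, 18, 13 and 11%. That is far below Step 2 if montelukast also helps run-in flushers, and above Step 3 if it does not.

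**The case against.** The strongest reply is that nothing is invalid here. Subjects are randomized before the run-in and take no randomized treatment during it, so run-in flushing is balanced in expectation and the chi-squared test holds its level. Flushing is a secondary endpoint with no stated power, and Protocol 16.4.4 planned only to summarize it. At 30 per arm power is modest with or without stratification. All of this stands, and it limits the point to efficiency.

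A reader might infer something stronger: that everyone already flushing at Day 0 is counted as an outcome that montelukast could not have prevented. The documents do not support that. SAP 7.3.4 is silent on flushing that is merely ongoing at Day 0, and the treatment-emergence rule in SAP 7.4.2.1, if it applies, excludes such flushing unless it worsened. A run-in flusher with a new episode after Day 0 does count, but one who stops flushing counts as a non-event, so the endpoint can register relief. The Day 0 definition matters little: the alert asks for a same-day start, for which Day 0 is the dosing day, and otherwise the extra time is about one day in ten weeks.

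Run-in flushing may also predict less well than assumed. Run-in length varies, and subjects who reach the threshold early may have taken only the starting dose. That shrinks the gain; in none of the scenarios computed did stratifying lower power.

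**Conclusion.** The point holds as a matter of precision. The planned test ignores a recorded pre-treatment variable that probably predicts the outcome. Under the assumed rates, stratifying removes 9% to 50% of the variance. The power gain at 59 per arm runs from about 1 to 16 points if montelukast halves flushing in both strata, and is under 2 points in those scenarios if it does nothing for run-in flushers. The direction is consistent across everything computed; the size rests on rates that the documents do not give.

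The documents do not support a claim of bias, of inflated type I error, or that prevalent flushers are certainly counted as outcomes. Nor do they support replacing the endpoint with new-onset or worsened flushing, which gains or loses power according to an unknown, namely whether montelukast relieves flushing in subjects who already have it. What is missing is a statement of which rule governs flushing ongoing at Day 0. Without it, SAP Table 28 and the flushing terms in SAP Table 33.1 could show different counts.

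**What to change.** In SAP 7.3.4:

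1. Keep the planned endpoint, flushing from Day 0 to Week 10 in the modified ITT population.
2. Replace the chi-squared test with a CMH test, and report a Mantel-Haenszel risk difference with its 95% confidence interval, stratified by any flushing adverse event (same preferred terms) with onset before the first montelukast/placebo dose, yes or no. Keep the crude proportions by arm as a descriptive line.
3. State whether the treatment-emergence rule of SAP 7.4.2.1 governs flushing that is ongoing at Day 0.
4. Report new-onset or worsened flushing after the first montelukast/placebo dose as a supportive summary only.
5. Confirm that the first dose of study treatment in Protocol 15.2.1 means the first DMF dose, as in Protocol Table 1, since the stratum depends on it.

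The cost is a few lines of SAP text and one derived flag. No new data, visits or subjects are needed. The change should be fixed before unblinding. At 30 per arm and q = 30% the smaller stratum holds about 0.3 × 30 = 9 subjects per arm, and the simulated CMH test kept its level there.

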7.3.5 Analysis methods-Exploratory endpoints

7.4 Safety Data

7.4.1 Safety analysis Population

The primary safety analysis population is the Montelukast/placebo safety analysis population. Selected analyses will also be summarized in the DMF safety analysis population.

7.4.2 Analysis Methods

Safety analyses will summarize all adverse events (AEs). In general, SAE and AEs will be analyzed based on incidence, defined as the proportion of subjects who had at least one occurrence of an event out of the number of subjects in the safety population.

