4.3. Additional Information

After initial eligibility has been confirmed at the Screening Visit, subjects will enter a 2-week (+14 days) Screening Period. At the end of this period, eligible subjects will return to the clinic for a Randomization Visit. The eligibility criteria will be rechecked, and additionally, the gastrointestinal (GI) symptoms noted in an electronic diary (eDiary) will be assessed. Individuals with Gastrointestinal Symptom Rating Scale (GSRS, Section 4.4) score of ≥ 5 in 1 question for 1 day, a GSRS score of >4 in 1 question for 2 consecutive days, or a GSRS score of \geq 3 in 1 question for 3 consecutive days will be discontinued and counted as screen failures. An eDiary compliance check will also be performed. Subjects will be required to be >75%compliant in the 14 days prior to randomization to remain eligible to participate in the study. Subjects who fulfill the eligibility criteria and meet the GI symptom assessment criteria will be randomized to 1 of 2 treatment arms. At this time, subjects will start commercial dimethyl fumarate (DMF) and will receive (but will not begin taking) their randomized study treatment. Subjects will then enter the DMF-GI Monitoring Period (up to 28 days). During this period, subjects will take DMF and note their daily GI symptoms in the eDiary. If at any time during this period, the GSRS scores noted are >3 in 1 question for 1 day or >2 in 1 question for 2 consecutive days, the subject will receive an alert through his/her eDiary to start taking the randomized study treatment the same day. Any subjects who do not reach this threshold during the 28-day period will be discontinued from the study. It will be the decision of the Investigator to continue with DMF therapy after the subject has been withdrawn from the study.

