6.2.3. Exploratory Endpoints

7. STUDY DESIGN

7.1. Study Overview

This multicenter study will evaluate the effect of montelukast on GI tolerability with relapsing forms of MS treated with DMF at approximately 50 study sites in the US. It is expected that approximately 295 subjects will be initially randomized to obtain approximately 118 subjects dosed with randomized study treatment (59 subjects dosed with randomized study treatment per treatment arm). Not all randomized subjects will be eligible to be dosed with randomized study treatment. Randomized subjects will be required to reach a predefined threshold of GI symptom severity before dosing with randomized study treatment will be initiated. Subjects who withdraw from the study after initiating randomized study treatment will not be replaced.

Subjects will enter a 2-week (+14 days) Screening Period and record pertinent information regarding GI-related events to allow characterization of background GI-related events using the eDiary. Subjects will be required to be \geq 75% compliant in the 14 days prior to randomization to remain eligible to participate in the study. Subsequently, eligible subjects will initially take DMF (120 mg twice daily orally for the first week, 240 mg twice daily orally thereafter) for up to 28 days (DMF-GI Monitoring Period) and record GI-related events in the eDiary. During this period, subjects will take DMF, GSRS scores will be monitored, and subjects who reach a specific threshold will receive an alert through the eDiary to start taking randomized study treatment (10 mg once daily montelukast or placebo) the same day in accordance with the prescribing and labeling information. Subjects who do not meet the threshold or do not demonstrate \geq 75% compliance with the eDiary in the 14 days prior to randomization will be discontinued. Subjects will also use the eDiary to record DMF dosing, randomized study medication dosing, and any symptomatic concomitant medications/procedures. Eligible subjects will return to the study site at Weeks 0, 2, 4, 8 and at Week 10 for evaluation by study site staff. Weeks 2, 4, and 8 will have a visit window of ± 2 days, and Week 10 will have a visit window of \pm 3 days. If more convenient for the subject, visits at Weeks 2, and 8 may be performed remotely by a contracted home health nurse. The Safety Follow-Up Telephone Interview will be conducted 2 weeks (±5 days) after the Week 10 study visit or date of the Early Termination (ET) Visit.

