7.2. Overall Study Duration and Follow-Up

The study period consists of a 2-week (+14 days) Screening Period, up to a total of 14 weeks of DMF therapy (including DMF-GI Monitoring Period and randomized treatment administration period), including 8 weeks of concomitant randomized study treatment (DMF + montelukast or DMF + placebo), and the Safety Follow-Up Telephone Interview. The duration of a subject's participation will be up to 18 weeks. Subjects who discontinue the study early will complete the same assessments specified for the Week 10 Visit. Refer to Section 1 for the timing of assessments to be performed in this study.

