Table 21: Summary of average change of GSRS score from baseline (Day 0) by repeated measures analysis, Day 1 to Weeks 1-8

Table 22: Summary of average change of GSRS score from baseline (Day 0) by repeated measures analysis, at 72 hours from the initiation of randomized study treatment (Day 1 - Day 3)

Table 23: Summary of primary endpoint by baseline demographic and disease characteristics

Table 24: Summary of average change of GI severity score from baseline (Day 0), repeated measures analysis, Day 1 to Day 10, by baseline demographic and disease characteristics

Table 25: Summary of average change of GI severity score from baseline (Day 0), repeated measures analysis, Day 1 to Week 10, by baseline demographic and disease characteristics

Table 26: Summary of proportion of subjects who take GI symptomatic therapy during the study

Table 27: Summary of proportion of subjects who discontinue DMF therapy due to GI-related adverse events from Day 0 to Week 10

Table 28: Summary of proportion of subjects who experience flushing events

Table 29: Summary of biomarker scores, changes and percent changes from Tecfidera baseline, by treatment group and visit, DMF safety analysis population

Table 30: Summary of biomarker scores, changes and percent changes from Montelukast baseline, by treatment group and visit, Montelukast/placebo safety analysis population

Table 31.1: Summary of selected hematology parameters, change and percent change from Montelukast baseline, by treatment group and visit, Montelukast/placebo safety analysis population

Table 31.2: Summary of selected hematology parameters, change and percent change from Tecfidera baseline, by treatment group and visit, DMF safety analysis population

Table 32.1: Summary of hematology abnormalities by CTC grades, by treatment group and visit, DMF safety analysis population

Table 32.2: Summary of hematology abnormalities by CTC grades, by treatment group and visit, Montelukast /placebo safety analysis population

Table 33.1: Incidence of adverse events by system organ class and preferred term, Montelukast/placebo safety analysis population

Table 33.2: Incidence of adverse events by system organ class and preferred term, DMF safety analysis population

Table 34.1: Incidence of serious adverse events by system organ class and preferred term, Montelukast/placebo safety analysis population

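### Crude AE incidence in the DMF safety population pools about 6 weeks of observation in some 60% of subjects with 13 to 16 weeks in the rest, so rates of later events are diluted, most clearly in Tables 37 and 38

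*Combined protocol and SAP*

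**What the plan says.** Subjects are randomized before starting DMF and take montelukast or placebo only if their GSRS scores reach a threshold. Protocol 7.2.4 says "The duration of the DMF-GI Monitoring Period will be up to 28 days", and then "Any subject who does not reach the GSRS threshold during the DMF-GI Monitoring Period will be discontinued". Protocol 4.3 has the same rule and adds "It will be the decision of the Investigator to continue with DMF therapy after the subject has been withdrawn from the study". Protocol 7.1 expects that "approximately 295 subjects will be initially randomized to obtain approximately 118 subjects dosed with randomized study treatment".

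SAP 7.1.2 defines two safety populations. The primary one is everyone with at least one dose of montelukast or placebo. The DMF safety population is everyone with at least one dose of DMF, so it keeps the subjects who never reached the threshold. AE collection runs from the first DMF dose to a telephone interview 2 weeks after the Week 10 or early-termination (ET) visit (Protocol 4.2, Table 1).

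SAP 7.4.2 defines incidence, in general, as the "proportion of subjects who had at least one occurrence of an event out of the number of subjects in the safety population". The visible text has no exposure-adjusted, period-specific or time-to-event AE analysis. In SAP 8, Tables 33.2, 34.2, 35.2, 36.2, 37 and 38 are AE tables in the DMF population. Tables 37 (severity) and 38 (relationship to study treatment or DMF) are listed for that population alone. Tables 29, 31.2 and 32.1 report biomarkers and hematology by visit in the same population, for example "Table 31.2: Summary of selected hematology parameters, change and percent change from Tecfidera baseline, by treatment group and visit, DMF safety analysis population". On early leavers, Protocol 7.2 says "Subjects who discontinue the study early will complete the same assessments specified for the Week 10 Visit".

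**The concern.** A crude proportion is easy to interpret when everyone is watched for about the same time. Here the design creates two groups with very different AE windows and puts both in one denominator. The resulting percentage describes neither 6 weeks nor 13 to 16 weeks of DMF; it is a mixture whose value depends on how many subjects reached the threshold.

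The consequence is sharpest for Table 38. A subject who never took montelukast or placebo cannot have an event caused by it, yet counts in the denominator for relatedness to study treatment. Without a dosed-subject version of that table, the listed outputs would understate how often events were judged related to the randomized drug.

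**Working it through.** **Inputs**
- 295 randomized, 118 dosed (Protocol 7.1).
- Monitoring up to 28 days (Protocol 7.2.4).
- Week 10 visit counted from the first randomized dose; telephone call 14 days after Week 10/ET (Protocol 4.2).
- Assumption: threshold reached between DMF day 7 and day 28. The documents give no distribution.
- Assumption: the same underlying risk in dosed and never-dosed subjects.

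**Planned split.** 118/295 = 0.40 dosed; 295 − 118 = 177, and 177/295 = 0.60 never dosed. The documents do not print the 60%; it follows from their figures. SAP 5 closes enrollment at about 60 dosed. If the ratio held, that would mean 60/0.40 = 150 randomized and 90 never dosed, with the same shares.

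**AE windows**
- Never dosed: 28 + 14 = 42 days (6 weeks).
- Dosed completers: trigger day + 70 + 14, giving 7 + 84 = 91 days to 28 + 84 = 112 days (13 to 16 weeks).
- Ratio: 91/42 = 2.2 to 112/42 = 2.7.

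**Dilution.** Let R be the risk over the full window T of a dosed subject.

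(a) Event arising only after never-dosed subjects leave observation: crude = 0.40 × R. A 10% risk prints as 4%. This factor is simply the dosed share, whatever that turns out to be.

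(b) Constant hazard: risk over 42 days = 1 − (1 − R)^(42/T), and crude = 0.40 × R + 0.60 × [1 − (1 − R)^(42/T)].

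| R | T = 91 days | T = 112 days |
|---|---|---|
| 5% | 3.4% (ratio 0.68) | 3.1% (0.63) |
| 10% | 6.8% (0.68) | 6.3% (0.63) |
| 30% | 21.1% (0.70) | 19.5% (0.65) |

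With looser windows of 12 to 16 weeks for dosed and 4 to 6 weeks for never-dosed subjects, and risks of 5% to 20%, the ratio runs from 0.55 to 0.72.

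(c) Event confined to the first 4 weeks of DMF: both groups are observed throughout, so the ratio is 1.

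**Table 38.** If 10% of dosed subjects have an event judged related to study treatment, the DMF-population figure is 0.40 × 10% = 4%.

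**By-visit tables, only if ET results are pooled with Week 10.** With attendance a among never-dosed subjects and one entry per dosed subject, their share of the row is 177a/(177a + 118): 60% at a = 1, 53% at a = 0.75 and 43% at a = 0.5. It exceeds half only if a is above 118/177 = 0.67. If ET results are kept apart, the share is 0%.

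**The case against.** The strongest reply is that the primary safety analysis is untouched. SAP 7.4.1 makes the Montelukast/placebo population primary, and only selected analyses use the DMF population. Tables 30, 31.1, 32.2, 33.1, 34.1, 35.1 and 36.1 cover dosed subjects, with treatment emergence counted from the start of montelukast or placebo (SAP 7.4.2.1). The late event in 10% of dosed subjects would print at about 10% in Table 33.1. This stands and limits the point to secondary outputs, but it does not reach Tables 37 and 38. The statement in SAP 8 that other tables may be added is no commitment to produce them in dosed subjects.

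The SAP also summarizes days on DMF in the DMF population (SAP 7.2.7, Table 8) and counts subjects dosed with each treatment (SAP 7.2.2). That discloses the imbalance without correcting any rate.

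It can be said that DMF events come early and so are not diluted. Case (c) grants this. But the early clustering described in Protocol 5.2 concerns GI events, and Protocol 15.2.1 sends nonserious GI events to the eDiary rather than the CRF. The documents give no reason to assume that all other AEs are early.

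Removal happens before randomized dosing and should be balanced between arms. That stands: no arm is favored.

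A reader might infer from the shared Week 10/ET column in the schedule of events that the Week 10 row of Tables 29, 31.2 and 32.1 will be mostly data from 4 weeks or less on DMF. The documents do not support stating that:
- No visible text pools ET with Week 10, and the body of SAP 7.4.2.2, where such a rule could sit, is not in the supplied text.
- Protocol 12 asks for the ET visit only where feasible, and of those who stop study treatment early.
- Biomarker sampling is optional.

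**Conclusion.** The point holds as a cheap improvement to secondary outputs. In the DMF safety population the crude AE percentage mixes windows of about 6 and 13 to 16 weeks. Absolute rates are diluted to 0.40 of the dosed-subject risk for late-only events and to about 0.63 to 0.70 under a constant hazard, and not at all for events in the first 4 weeks. Differences between arms that arise after dosing shrink too, but with no directional bias. Tables 37 and 38 are the clearest case, because no dosed-subject version is listed.

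The size rests on several assumptions:
- The 60% is a planning ratio that includes anyone lost before dosing, and the threshold changed after protocol version 1 (SAP 3.1).
- The windows assume completion and, for never-dosed subjects, a follow-up call.
- The 28 days caps on-study DMF only, since DMF may continue off study.

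The inference that the late laboratory and biomarker row consists mainly of early samples is not established. It would need both pooling of ET with Week 10 and attendance by more than two thirds of never-dosed subjects. What remains is a request to make the assignment rule explicit.

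**What to change.** 1. In Tables 33.2, 34.2, 35.2, 36.2, 37 and 38, show dosed and never-dosed subjects separately. Beside the crude percentages, give exposure-adjusted rates per patient-year, using time under AE observation as the denominator. The rates recover the hazard only if it is constant; the split is still needed if it changes with time on DMF.
2. Produce Tables 37 and 38 in the Montelukast/placebo safety population as well, and use that denominator for relatedness to study treatment.
3. In Tables 29, 31.2 and 32.1, keep never-dosed subjects' ET samples out of the Week 10 row and assign them by days since first DMF dose. If SAP 7.4.2.2 already does this, no change is needed.

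The cost is a few sentences of SAP text, some extra programming and longer tables. No new data are required.
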